A global evaluation of the status of the area where the study implants were placed will be recorded using gingival and plaque indices. The **gingival index** will be ranked as follows: (0) Normal gingiva; (1) Mild inflammation, slight change in color, slight edema, no bleeding on probing; (2) Moderate inflammation, redness, edema and glazing, bleeding on probing; (3) Severe inflammation, marked redness and edema, ulcerations; tendency toward spontaneous bleeding.

The criteria for **plaque index** are as follows: (1) No plaque in gingival area; (2) No plaque visible by the unaided eye, but plaque is made visible on the point of the probe after it has been removed across surface at entrance of gingival crevice; (3) Marginal area is covered with a thin to moderately thick layer of plaque; deposit is visible to the naked eye; (4) Heavy accumulation of soft matter, the thickness of which fills out a niche produced by gingival margin and tooth surface; interdental area is stuffed with soft debris.

EVALUATION CRITERIA

Implant Integration Success

An implant will be considered successful if it is immobile at specific points in time. Additionally, long-term implant success will be achieved when tested with instrument pressure at follow-up evaluations with no evidence of persistent peri-implant radiolucency, no persistent or irreversible signs and symptoms of pain, infection, neuropathies, or paresthesia.

Additionally the correlation of initial stability (as reflected in the Insertion Torque Profile) and clinical success will be assessed. The individual implant will be considered the experimental unit. The Insertion Torque Profiles for failed implants will be compared with those from successful implant cases to determine if this baseline variable is predictive.

Radiological Crestal Bone Level Changes

Bone levels measured at three and six month, and all follow-up intervals from both treatment groups will be compared to those measurements observed at the time of implant placement surgery to derive *changes from baseline* values. Differences between groups will be calculated and used to determine if the crestal bone changes are different between groups. A difference of 5% will be considered relevant.

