Secondary efficacy parameters will be prosthesis survival and procedural success. For each patient, survival time after study surgery will be calculated by the duration of failure-free, intervention-free, duration of support of a prosthesis. Implant survival curves will be estimated for the Test and Control treatment group and these will be compared using the Log Rank or Wilcoxon tests. Survival rates at six months (Study Visit 6), one-year (Study Visit 7) and 5 years (visit 11) will be computed for each treatment group, and compared using chi-square. The sample size determinations were based upon survival to the five-year point as a measure of efficacy.

A secondary outcome question of this study is the equivalence in the changes in alveolar crestal bone between the modified implant (T3) and its predecessor the Certain™ implant. In previous studies of Biomet3i implants (Calvo-Guirado 2011, Zetterqvist 2009; Östman et al. 2010), crestal bone change-from-baseline values have ranged from a mean of 0.37 mm to 1.2 mm at the six month (Visit 6) time point. For purposes of this study there will be an assumption that the control implant will have a change-from-baseline mean value of 0.75 mm at the 6 month (Visit 6) time period. To declare equivalence the Test implant system will need to have a crestal bone change-from-baseline mean bone level regression of 0.75 ± 0.15 mm; or to declare superiority a mean value of 0.55 mm or lower. For the functional evaluation of crestal bone regression will be determined for each of the treatment groups at 3 months (Visit 5), six months (Visit 6) and at each of the annual study visits. The significance of these changes from baseline will be evaluated at each time point using a paired t-test or a Wilcoxon signed rank test. At each time point the treatment groups will be compared using the analysis of variance or the blocked Wilcoxon test, as appropriate. Analysis to determine association with other variables will use “exact” rather than “asymptomatic” methods where necessary.

The Test and the Control implants will be considered the experimental units. The influence of the length and diameter of the implants as a covariate on survival will be determined during the analysis. The comparability of the Test and Control treatment groups will be determined with regard to demographic

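### The 5% relevance rule for crestal bone has no stated base and, on its natural reading, conflicts at Month 6 with the ± 0.15 mm equivalence range

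*Combined protocol and SAP*

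**What the plan says.** Two sections of the combined protocol and SAP set thresholds for crestal bone change from baseline.

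**Evaluation Criteria, Radiological Crestal Bone Level Changes.** The measurements covered are "Bone levels measured at three and six month, and all follow-up intervals from both treatment groups", each compared with the level at implant surgery. The section continues: "Differences between groups will be calculated and used to determine if the crestal bone changes are different between groups". It ends: "A difference of 5% will be considered relevant". No base for the percentage is given.

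**Statistical Analyses.** For Month 6 the section assumes that "the control implant will have a change-from-baseline mean value of 0.75 mm at the 6 month (Visit 6) time period". The rule for equivalence is: "To declare equivalence the Test implant system will need to have a crestal bone change-from-baseline mean bone level regression of 0.75 ± 0.15 mm". The sentence goes on: "or to declare superiority a mean value of 0.55 mm or lower". As background it reports that in earlier studies of the manufacturer's implants "crestal bone change-from-baseline values have ranged from a mean of 0.37 mm to 1.2 mm at the six month (Visit 6) time point".

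The Statistical Analyses section also calls implant survival differences above 5% clinically relevant. That is a separate rule for a separate endpoint. Nothing links the two crestal bone rules or says which one governs.

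**The concern.** Both rules concern the same measurement and both cover Month 6. One says when a difference between the groups matters; the other says when the test implant may be called equivalent. These should fit together, because an equivalence margin is normally no wider than the smallest difference that the plan regards as relevant. Here the margin appears to admit differences up to four times the relevance threshold.

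At stake is how the Month 6 crestal bone result is described. Preservation of crestal bone is named in the trial title alongside implant survival. The Study Design section counts crestal bone regression in the primary endpoint, while Statistical Analyses treats it as a secondary question. Under either status it supports a comparative claim, and the plan leaves open whether a moderate difference would be reported as relevant or as equivalence.

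**Working it through.** The plan gives no derived figure to reproduce on this point, so the check is direct arithmetic on its stated thresholds.

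**Inputs**
- Relevance threshold: 5%, base not stated (Evaluation Criteria).
- Assumed control mean change at Month 6: 0.75 mm (Statistical Analyses).
- Equivalence range for the test mean: 0.75 ± 0.15 mm (Statistical Analyses).
- Superiority limit for the test mean: 0.55 mm or lower (Statistical Analyses).
- Earlier mean changes at six months: 0.37 to 1.2 mm (Statistical Analyses).
- Implant lengths: 8.5 to 13 mm (Materials and Methods).

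**Step 1. Put both rules on one scale, with the control mean at 0.75 mm**
- Relevance threshold: 0.05 × 0.75 = 0.0375 mm.
- Equivalence tolerance: 0.15 / 0.75 = 20%.
- Ratio: 0.15 / 0.0375 = 4.
- Superiority distance: 0.75 − 0.55 = 0.20 mm; 0.20 / 0.75 = 26.7%.

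**Step 2. Find the test means that meet both rules**
- Relevant: at or below 0.75 − 0.0375 = 0.7125 mm, or at or above 0.75 + 0.0375 = 0.7875 mm.
- Equivalent: 0.75 − 0.15 = 0.60 mm to 0.75 + 0.15 = 0.90 mm.
- Both: 0.60 to 0.7125 mm and 0.7875 to 0.90 mm.
- Width of the overlap: 0.1125 + 0.1125 = 0.225 mm, out of an equivalence range of 0.30 mm; 0.225 / 0.30 = 75%.
- Example: a test mean of 0.85 mm differs by 0.10 mm (0.10 / 0.75 = 13.3%). It is relevant under one section and equivalent under the other.

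**Step 3. Vary the base of the 5%**

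| Base | 5% of base | Compared with 0.15 mm |
|---|---|---|
| 0.37 mm (lowest cited mean) | 0.0185 mm | smaller |
| 0.75 mm (assumed control mean) | 0.0375 mm | smaller |
| 1.2 mm (highest cited mean) | 0.06 mm | smaller |
| 8.5 mm (shortest implant) | 0.425 mm | larger |
| 13 mm (longest implant) | 0.65 mm | larger |

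The two thresholds would coincide only on a base of 0.15 / 0.05 = 3.0 mm. Any mean change in the cited range gives a relevance threshold well inside the equivalence tolerance.

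**Step 4. Vary the observed control mean**

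The equivalence range is fixed at 0.60 to 0.90 mm whatever the control group shows. Suppose the control mean is 0.60 mm and the 5% is taken of that value. Differences are then not relevant only for test means between 0.57 and 0.63 mm (0.60 ± 0.03), so test means from 0.63 to 0.90 mm carry both labels. A test mean of 0.85 mm would count as equivalent although it is 0.85 − 0.60 = 0.25 mm from control. The limits of the overlap move with the control mean, and the fixed target can admit differences larger than 0.15 mm.

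**The case against.** The strongest defence is that the 5% has no stated base, so the conflict depends on how it is read. On implant length the threshold would be 0.425 to 0.65 mm, and no difference within 0.15 mm would be called relevant. That is correct as arithmetic. However, the 5% sentence directly follows the comparison of bone changes between groups, and nothing in the documents ties it to implant length. The control mean change is the natural base. This remains an inference, and the missing base is a defect in its own right.

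A second defence is that the rules use different statistics. One concerns the observed difference between groups; the other limits the test mean against an assumed control value, at Month 6 only. This stands. The figures of 0.0375 to 0.15 mm and 75% therefore hold exactly only when the control mean is 0.75 mm. It does not remove the conflict, because both rules would be applied to the same Month 6 data.

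A third defence is that the relevance sentence triggers no test, and that only the Statistical Analyses section declares a result. That limits the consequence to interpretation.

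A reader might also infer more than the documents support:
- **That every equivalent result is also relevant.** Differences below 0.0375 mm, with the control at 0.75 mm, are equivalent and not relevant.
- **That the 5% was carried over from the survival rule.** This is plausible, but the documents do not say so.
- **That the two rules were meant to allow a choice of label.** The text shows an opportunity, not an intention.
- **That the interval from 0.55 to 0.60 mm, neither equivalent nor superior, is an error.** An indeterminate zone between two claims is allowable; it only needs a statement of how it will be reported.

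**Conclusion.** The point holds with its conditions attached. The plan calls a 5% difference in crestal bone change relevant without saying of what. Read against the control mean change, this conflicts at Month 6 with an equivalence tolerance of 20%. With a control mean of 0.75 mm, the double label covers differences of 0.0375 to 0.15 mm in either direction, which is 75% of the equivalence range.

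The conclusion rests on two assumptions: that the base is the control mean change, and, for the exact limits, that the control mean equals the assumed 0.75 mm. The first is supported by context but not stated. Across the cited means the 5% threshold never exceeds 0.06 mm, so the choice among those bases does not matter.

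The plan should be amended on this point. It does not threaten the survival analysis or the sample size, which the plan bases on five-year survival.

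**What to change.** Reconcile the two sections.

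1. Remove the 5% sentence from Radiological Crestal Bone Level Changes, and keep the rule of more than 5% for implant survival only.
2. Use one pre-specified margin in millimetres, with a justification. The plan's own 0.15 mm is one candidate. If the sponsor prefers to keep 5%, it must define the base and narrow the equivalence range to match.
3. State that the margin applies to the observed between-group difference in mean change from baseline, not to the distance of the test mean from an assumed 0.75 mm. Express the superiority limit on the same scale; the present figures imply 0.20 mm below control.
4. Name the visits covered: Month 6 for the equivalence or superiority claim, with Month 3 and the annual visits either descriptive or held to the same margin.
5. State how a favourable difference between the equivalence and superiority limits will be reported.

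Possible wording, if 0.15 mm is retained: *Equivalence at Month 6 is judged on the observed test-minus-control difference in mean crestal bone change from baseline, with a margin of ± 0.15 mm. Superiority requires a difference of at least 0.20 mm in favour of test. A favourable difference between these limits supports neither claim. Other visits are descriptive.*

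The cost is an edit to both sections. Step 3 changes a fixed-target rule into a between-group rule, so it should be recorded as a change of substance. Differences of about 0.04 to 0.15 mm could no longer be presented as relevant.

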- Probably related - an event that follows a known or suspected response pattern, is confirmed by improvement upon stopping or reducing treatment, and cannot be reasonably explained by the known characteristics of the patient's clinical state.
- Definitely related - an event that follows a known or suspected response pattern, is confirmed by improvement upon stopping or reducing treatment, and reappears upon repeated exposure.
- Unknown - relationships for which insufficient information exists.

Failure to use an implant due to improper placement is not an adverse event in the absence of pathology, but is censored data for the survival analysis and must be reported on the Implant Failure Form (ICF).

Medical Adverse Events

Death, serious illness or major trauma, whether implant success is affected or not, is an adverse event and must be reported on the Medical Event form (AME). A medical adverse event will be assessed based on causality (criteria described in dental adverse event section) and severity. Severity criteria are described as follows:

- Mild - the adverse reaction does not interfere in a significant manner with the patient's normal functioning level.
- Moderate - the adverse reaction produces some impairment of functioning but is not hazardous to health; may be uncomfortable.

- Severe - the adverse reaction produces significant impairment of functioning or incapacitation and is a definite hazard to the patient's health; this can lead to 1) death or decreased life expectancy, 2) an immediate life-threatening event, 3) inability to resume usual life pattern, 4) significant disability or incapacity.

STATISTICAL ANALYSES

The primary efficacy parameter will be the duration of implant survival (failure-free utilization or lack of mobility) from implant placement. The fraction of surviving implants and cases at the completion of 1, 2 and 5 years of function will be evaluated. Implant survival differences of >5 % will be considered clinically relevant. Clinical outcomes will be evaluated by clinical signs and symptoms of implant failure and dental and medical events.

Secondary efficacy parameters will be prosthesis survival and procedural success. For each patient, survival time after study surgery will be calculated by the duration of failure-free, intervention-free, duration of support of a prosthesis. Implant survival curves will be estimated for the Test and Control treatment group and these will be compared using the Log Rank or Wilcoxon tests. Survival rates at six months (Study Visit 6), one-year (Study Visit 7) and 5 years (visit 11) will be computed for each treatment group, and compared using chi-square. The sample size determinations were based upon survival to the five-year point as a measure of efficacy.

A secondary outcome question of this study is the equivalence in the changes in alveolar crestal bone between the modified implant (T3) and its predecessor the Certain™ implant. In previous studies of Biomet3i implants (Calvo-Guirado 2011, Zetterqvist 2009; Östman et al. 2010), crestal bone change-from-baseline values have ranged from a mean of 0.37 mm to 1.2 mm at the six month (Visit 6) time point. For purposes of this study there will be an assumption that the control implant will have a change-from-baseline mean value of 0.75 mm at the 6 month (Visit 6) time period. To declare equivalence the Test implant system will need to have a crestal bone change-from-baseline mean bone level regression of 0.75 ± 0.15 mm; or to declare superiority a mean value of 0.55 mm or lower. For the functional evaluation of crestal bone regression will be determined for each of the treatment groups at 3 months (Visit 5), six months (Visit 6) and at each of the annual study visits. The significance of these changes from baseline will be evaluated at each time point using a paired t-test or a Wilcoxon signed rank test. At each time point the treatment groups will be compared using the analysis of variance or the blocked Wilcoxon test, as appropriate. Analysis to determine association with other variables will use “exact” rather than “asymptomatic” methods where necessary.

The Test and the Control implants will be considered the experimental units. The influence of the length and diameter of the implants as a covariate on survival will be determined during the analysis. The comparability of the Test and Control treatment groups will be determined with regard to demographic

variables (including age, gender) and variables relating to the severity of disease (such as existing dental pathology and dental hygiene). For the continuous variables age and evaluations of oral hygiene and the gingival biotype, the groups will be compared using either analysis of variance or blocked Wilcoxon, as appropriate. For the qualitative variables, sex, smoking habit, existing dentition, concomitant conditions, a chi-square contingency table analysis will be used. Analysis to determine association with other variables will use "exact", rather than asymptotic methods where necessary.

All dental and medical events will be tabulated. Treatment groups will be compared using chi-square with regard to the number of patients in each group who experience those events most frequently and are assessed by the investigator as being probably or definitely related to the investigational treatment. Statistical significance will be declared if the two sided p-value is > 0.05 .

Calvo-Guirado JL, Gómez-Moreno G , López-Marí L, Guardia J, Negri B, Martínez-González JM. Crestal bone loss evaluation in osseotite expanded platform implants: a 5-year study. Clin Oral Impl Res 2011 21 MAR 2011
DOI: 10.1111/j.1600-0501.2010.02130.x

Östman PO, Wennerberg A, Albrektsson T. Immediate occlusal loading of NanoTite Prevail implants: a prospective 1-year clinical and radiographic study. Clin Implant Dent Relat Res. 2010 Mar;12(1):39-47.

Records / Data Retention

Case Report Forms (CRFs) will be prepared by 3i for the collection of data. These forms will be used for the entire duration of the study. The original of the completed CRF will continuously be collected by the study monitor for analysis and storage. Only original radiographs (or digital images saved on a disc) will be accepted and maintained by the study sponsor. Investigators will keep a copy of the CRFs and will maintain these records for at least three years.

CRFs are required for all individuals enrolled in the study. These should be filled out in ballpoint pen and be legible and complete. Errors should be lined out, such that the information being lined out can still be seen. Initial and date the correction. Do not use correction fluids. CRFs will be considered complete when all data queries have been fully addressed.

All original CRFs are the property of Biomet 3i. They may not be made available to a third party in any fashion, with the exception of authorized representatives of appropriate government agencies or business partners, who must accept the same level of confidentiality.

Protocol Amendments

Any proposed change to the protocol is to be discussed with the clinical monitor in a timely manner. Once both the investigator and the sponsor have accepted the changes, a written addendum to the protocol or a revised protocol will be sent to the investigator for signature. Copies of addenda and revised protocols will be kept by both parties in their respective files.

Protocol Deviations and Violations

Occasionally during the study, deviations from the procedures established in the protocol may occur. Any deviation from the protocol is reason to contact a clinical monitor without delay. The deviation will be documented on the appropriate data form. Enrollment and treatment of patients who do not meet Admission Criteria will be considered a protocol violation.

Data confidentiality, Verification and Monitoring

A Biomet 3i Study Monitor will be assigned to monitor the study. Before the start of the study, the monitor will contact the principal investigator to ensure that the protocol and study logistics are well-understood. Specific instructions as to the proper completion of the clinical data forms will be provided. The monitor may contact the investigator on a monthly basis for verbal updates.

At various time points in the study, a review of patient records may be needed to ensure accuracy of data. In this case study patient charts must be made available to the study monitors during site visits.

SIGNATURE PAGE

**TITLE: A Prospective, Randomized-Controlled Evaluation of
Biomet3i's T3-Surface Configuration on the Certain Implant
System for Implant Survival and the Preservation of Crestal
Bone.**

CODE NAME: OAK

PROTOCOL #: 3023

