This will be a prospective, randomized-controlled study in which qualified patients with partial edentulism will be treated with at least two dental implants. Implant sites will be randomly assigned to receive either a test (T3 Nanotite Certain Tapered Prevail - BNPT) or control (Nanotite Certain Tapered - NINTxx) implant (80:20 – test – control randomization ratio). All implants will be placed in a single-stage manner using torque-indicating instruments to document the torque-insertion profile. At implant placement surgery test implants will receive Encode healing abutments whereas control implants will be provisioned with prefabricated or standard abutments. For the test group an Encode Level Impression will take place at 10 weeks and individual final abutments and prosthesis placement at 3 months following implant placement surgery. A fixture level impression will be taken for control implants at week 10, followed by final restorations at month 3. All implants will be allowed to integrate without occluding forces and all restorations will be cemented. Resonance frequency assessment procedures will be done at implant placement surgery and at prosthesis insertion. Cumulative success rate and crestal bone regression will be the primary study endpoint. Enrollment will continue until 100 patients have completed final prosthetic treatment at the participating study centers. Additional control cases will be derived from on-going clinical trials of the NINT implants matched with the prospective study control group for baseline variables, restorative type (STR, fixed bridges), and implant dimensions. The additional control cases will bring the test and control groups to a 1:1 ratio and allow for more powerful analyses.

Study (null) hypothesis:

The functional success (survival and success rate) of the T3 implant to maintain integration and support of prostheses in this study will be no different than of the control implant. Moreover there crestal bone changes that take place after placement and loading of the T3 Certain Tapered Prevail (BNPTxxx – test implant) and Certain Tapered (NINTxx - control implant) will be the same.

[figure not shown]
MATERIALS AND METHODS

Implants with similar geometry but with different surface roughness will be evaluated. All implants are titanium root-form dental implants. The test implant has an integrated platform switch feature, whereas the restorative components of the control implant will be matched.

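### Survival is compared only by tests of zero difference, so a non-significant result cannot show that T3 lies within the plan's own 5% threshold

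*Combined protocol and SAP*

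**What the plan says.** Under STUDY DESIGN, the statement headed "Study (null) hypothesis" says that the functional success of T3, meaning survival and success rate, "will be no different than of the control implant". No alternative hypothesis is written for survival.

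STATISTICAL ANALYSES opens with: "The primary efficacy parameter will be the duration of implant survival (failure-free utilization or lack of mobility) from implant placement". It then adds: "Implant survival differences of >5 % will be considered clinically relevant". The figure has no stated direction, is not called a margin, and is not said to be absolute or relative.

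The same section gives two between-group analyses of survival. The first is "Implant survival curves will be estimated for the Test and Control treatment group and these will be compared using the Log Rank or Wilcoxon tests". The second takes the rates at six months, one year and five years, which "will be computed for each treatment group, and compared using chi-square". Crestal bone, in contrast, gets a numerical criterion there: equivalence requires a test mean of 0.75 ± 0.15 mm. Survival has no counterpart.

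**The concern.** Log-rank, Wilcoxon and chi-square tests all ask whether the data contradict a difference of zero. When they do not, the difference may be small, or there may be too few failures to see a large one. The plan has no step that separates the two. The 5% figure enters no test, interval or decision rule, so at most it can be held against a point estimate.

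The question concerns a new implant against its predecessor and the primary parameter. Failures are probably few and the randomised control arm is small. In that setting non-significance is the expected result even when T3 is worse by more than the plan calls relevant. Correcting the power statement, the analysis unit or the p-value wording would not cure this.

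**Working it through.** **No figure to reproduce.** STATISTICAL ANALYSES says the sample size rests on five-year survival but gives no rate, difference, power or formula.

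**Inputs from the protocol.** 100 patients with at least two implants each (Patient Sample); 80:20 allocation (Randomization); non-randomised controls added to reach 1:1 (STUDY DESIGN). Taking exactly two implants per patient:
- randomised comparison: 80 × 2 = 160 test and 20 × 2 = 40 control implants;
- topped-up comparison: 160 and 160.

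**Assumed.** Control survival of 93, 95, 97 or 98% at 5 years; independent implants; no dropout; 5% read as absolute points; two-sided 5% level. The significance rule is printed as "Statistical significance will be declared if the two sided p-value is > 0.05"; it is read here as < 0.05, and the misprint is a separate matter.

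**Step 1: how often a real deficit is non-significant.** The test is the Pearson chi-square, z = (pC − pT) / √[p̄(1 − p̄)(1/nC + 1/nT)], where p̄ is pooled survival. Binomial probabilities are summed over all outcomes with |z| ≤ 1.96.

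| Control survival | 160:40, deficit 5 / 8 / 10 points | 160:160, deficit 5 / 8 / 10 points |
|---|---|---|
| 93% | 90 / 77 / 66% | 67 / 36 / 20% |
| 95% | 90 / 75 / 62% | 61 / 28 / 13% |
| 97% | 91 / 71 / 55% | 49 / 18 / 7% |
| 98% | 93 / 69 / 50% | 40 / 11 / 4% |

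Simulated log-rank tests agree at 5 points: about 90-93% for 160:40, and 66 / 61 / 49 / 39% for 160:160.

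Sensitivity: 15% loss and a design effect of 1.1 (both assumed) give effective sizes of 160 × 0.85 / 1.1 ≈ 124 and 40 × 0.85 / 1.1 ≈ 31. A 5-point deficit is then missed in about 93-97% (124:31) and 53-68% (124:124) of trials at 95-98% control survival.

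**Step 2: one possible result.** Suppose 39/40 control and 146/160 test implants survive. The deficit is 97.5 − 91.25 = 6.25 points, above the threshold. Pooled survival is 185/200 = 0.925, so chi-square = 0.0625² / [0.925 × 0.075 × (1/40 + 1/160)] = 1.80 and p = 0.18. The Newcombe 95% interval for the deficit runs from −4.7 to 12.0 points. The test reports no significant difference; the interval shows that the trial cannot tell.

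**Step 3: what an interval rule does.** Requiring the lower 95% limit (test minus control) to exceed −5 points wrongly passes a true 5-point deficit in about 1-4% of trials, across Wald and Newcombe intervals.

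When survival is truly equal at 95%, the half-width is 1.96 × √[0.95 × 0.05 × (1/nC + 1/nT)]:
- 160:40: 1.96 × 0.0385 = 7.6 points;
- 160:160: 1.96 × 0.0244 = 4.8 points.

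The chance of excluding a 5-point deficit is then Φ(0.05/SE − 1.96):
- 160:40: Φ(1.298 − 1.96) = 25%;
- 160:160: Φ(2.052 − 1.96) = 54%.

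Exact enumeration with the Newcombe interval gives 37% and 49%.

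**The case against.** The strongest reply is that the statement is labelled a null hypothesis. A null of no difference is conventional, and the log-rank and chi-square tests match it formally. That stands. A reader might infer that the sponsor plans to report a non-significant test as confirming sameness, but the documents never say what will be concluded from one. The defect is the missing rule, not a written false conclusion.

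A reader might also infer that a relevant deficit would usually be missed. For the randomised comparison that is fair: even at 10 points, half or more of trials are non-significant. It does not carry over to the planned 1:1 comparison. There the miss rate is below half at 5 points once control survival reaches about 97%, and only 4-20% at 10 points. A true deficit of exactly 5 points also sits on the plan's boundary, since only differences above 5% count as relevant; hence the 8- and 10-point results. The added controls are not randomised, however, so their extra power may come with bias.

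Nor is it right that holding the point estimate against 5 points does no better than the test. In the randomised comparison a true 5-point deficit is observed as 5 points or less in about 51% of trials, against about 90% non-significant. The near-half figure is almost automatic when the truth lies on the threshold, and a point estimate still carries no statement of uncertainty.

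Finally, calling 5% a non-inferiority margin goes beyond the text. The interval can be read against the plan's own threshold without claiming that a non-inferiority design was intended.

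**Conclusion.** The concern holds in this form: survival, the primary parameter, is analysed only by tests of zero difference, and nothing relates the estimated difference or its uncertainty to 5%. Non-significance cannot support a claim that survival is within 5%. This follows from the text and needs no assumption about rates.

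The size does depend on assumptions: control survival of 93-98%, two independent implants per patient and no dropout. On these, the chi-square test is non-significant in 90-93%, about 69-77% and 50-66% of randomised comparisons at true deficits of 5, 8 and 10 points. For the topped-up comparison the ranges are about 40-67%, 11-36% and 4-20%. The problem is therefore severe for the randomised comparison and moderate for the 1:1 comparison, where it is concentrated near the threshold. Because it governs the primary conclusion about a new device, the rule should be written before the data are analysed.

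**What to change.** In STATISTICAL ANALYSES:

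1. Report the 5-year Kaplan-Meier survival difference, test minus control, with a two-sided 95% confidence interval. Prespecify an interval method that allows for implants clustered within patients and suits few failures.
2. Show the randomised comparison separately from the topped-up one.
3. State that the 5% threshold is in absolute percentage points. Conclude that a clinically relevant deficit is excluded only if the lower limit is above −5 points. Otherwise make no claim of no difference, and report the result as inconclusive unless the interval shows a deficit.
4. Keep the log-rank test as a test of difference, and state that non-significance is not evidence of no difference.

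The cost is wording and one interval from data already collected; no patients are added. The price is that an inconclusive result is likely. At equal 95% survival and before clustering, a 5-point deficit would be excluded in only about 25-37% of trials at 160:40 and 49-54% at 160:160, depending on the interval method. For 80% power under the same assumptions, the control arm would need (1.96 + 0.84)² × 0.0475 × (1 + 1/k) / 0.05² implants, with k test implants per control. That is 187 controls and 935 implants in all at 4:1, or 299 and 598 at 1:1, against about 200 randomised implants planned. If the sponsor does not enlarge the trial, the protocol should say plainly that it may not be able to exclude a relevant deficit.
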